Endpoints. The intervention will be delivered per protocol until one of the following endpoints is met (whichever occurs first): 1) ETT removed (extubation); 2) tracheostomy performed; 3) 14 days of enrollment; or 4) other exclusion criterion met (e.g., rescue ventilation). *Extending the intervention to 14 days will allow us a better opportunity to address the secondary aim of VAC. At the study site, the median time to tracheostomy is 8 days; 85% of patients on prolonged MV undergo a tracheostomy by Day 14.*¹¹² *This duration of enrollment is longer than that reported in other intervention studies,*^{19,73,109} *and will allow us to test the effect of the intervention on both microaspiration and VAC prevention for an extended period. Subjects must be enrolled at least 36 hours to be included in analysis. Since the duration of MV varies and we want to assess the effect of our intervention on preventing microaspiration, we determined (with input from consultants) that a minimum enrollment of 36 hours would provide adequate samples to address the primary aim.*

Measurement of Primary and Secondary Outcome Variables

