VAC. VAC will be determined using the CDC/NHSN criteria (Figure 6, blue boxes).¹⁶ We will assess ventilator data (FiO₂ and PEEP) daily from the medical record to assess for worsening oxygenation status. Per consultation with [name], we will assess for VAC for 2 days beyond the last intervention. To address Aim 2 and hypotheses 2.1 and 2.2, we will record VAC as positive or negative. We will also record the time to VAC in days (0.1 day increments). Determination of VAC will be made by our intensivist co-investigator. The CDC/NHSN algorithm proceeds to determine if VAC is infection-related (grey part of algorithm).¹⁶ *Our primary endpoint is VAC as a broad complication that includes both infectious and noninfectious etiologies; however, we will also report possible and probable VAP in our analyses as applicable.*

Tracheal/Oral Ratio of α -Amylase. To address Aim 3 and hypothesis 3.1, the ratio of the tracheal value to the oral value of α -amylase for each paired sample will be calculated.

Training and Data Management

Personnel Training and Fidelity. The PI will be responsible for training and will be assisted by the PD in ensuring that all personnel are knowledgeable in their roles. At the beginning of the study, the PI and PD will develop a comprehensive study Operations Manual, which will include procedures and checklists for subject enrollment, delivery of the NO-ASPIRATE and usual care/sham interventions, data collection, and ongoing

reporting related to the study (e.g., IRB and DSMB). All study personnel will complete the required CITI training on protection of human subjects and will sign confidentiality agreements.

The PI and PD will train the RAs in all study-related procedures. Initial training for the NO-ASPIRATE intervention, the usual care/sham intervention, and specimen collection will be conducted in a simulation laboratory, followed by observation in the clinical setting. Inter-rater reliability will be established for delivery of the NO-ASPIRATE and usual care/sham interventions, and for review of the medical record for study-related data. A kappa of at least .90 will be achieved between data collectors. To ensure treatment fidelity, additional re-assessment and related training will be done every 6 months using a standard observation checklist.

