Subjects will be randomly assigned to each of the two treatment groups at 1:1 ratio. Before analysis, data will be carefully examined for accuracy. Every effort will be made to avoid missing data. Subject characteristics at baseline will be examined to ensure a sound balance on demographic variables between the two groups. For continuous demographic variables, independent two-sample *t* tests will be used to detect differences between the two groups. For categorical demographic variables, the Pearson's chi-square test will be used to examine differences between the two groups. If subject subsets are found to be significantly different for a demographic variable, then this variable will be included into the statistical models. All planned analyses will be based on the intent-to-treat (ITT) population, which consists of all subjects who have been randomized into the NO-ASPIRATE or usual care group. In all analyses, an alpha level of 0.05 will be used.

[figure not shown]

Figure 6. Algorithm for Determining VAC

Aim 1. To compare the effects of the NO-ASPIRATE intervention versus usual care on microaspiration of gastric and oral contents in critically-ill intubated patients. Hypothesis 1.1.

Subjects in the NO-ASPIRATE group will have a significantly lower percentage of tracheal secretions with α -amylase present as compared to those in the usual care group. **Analysis 1.1.** Percentages of tracheal secretions α -amylase present for both groups will be computed. The percentage difference between the two groups will be calculated along with the 95% confidence interval for the percentage difference. The logistic regression including covariates of interest will be used to assess the percentage difference adjusting for the prognostic covariates.

Hypothesis 1.2. Subjects in the NO-ASPIRATE group will have a lower mean value of α -amylase in tracheal secretions as compared to those in the usual care group. **Analysis 1.2.** Values of α -amylase in tracheal secretions will be collected for each subject every 12 hours during study. Treatment effect based on these values over time will be evaluated by the generalized linear models using the generalized estimating equation (GEE) method.^{124,125} In addition, the generalized linear models with prognostic covariates of interest will be used to assess change in mean values of α -amylase over time adjusting for prognostic covariates.

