The research materials for this study include data from the subject's medical record and observation. Oral secretion and sputum specimens (endotracheal aspirate) for assays of α -amylase will be obtained at baseline and every 12 hours for up to 14 days. Specimens will be discarded after analysis. Demographic and physiological data will be obtained daily from the EMR. Data to determine presence of VAC will be obtained daily and for 2 days after the last intervention has been delivered. VAC-related data will be obtained from the EMR.

Describe any data that will be collected from human subjects for the project described in the application.

At baseline (enrollment), we will collect demographic, physiological, and ventilator data (Table 1). Data include age, gender, ethnicity, race, diagnosis, ETT information (type of tube and time of intubation), and severity of illness data. Physiological data will be obtained from the medical record at time of enrollment and per schedule (either daily or every 4 hours): temperature, vital signs, and sedation score. Information related to types of enteral tubes and nutritional support will be collected. Ventilator data will include mode of ventilation, set respiratory rate, positive end expiratory pressure, pressure support, and fraction of inspired oxygen. Ventilator data will assist in determining VAC. Temperature and results of tracheal aspirate cultures will be obtained from

the EMR for secondary analysis of infection or non-infection related VAC. Upon completion of the study, additional outcome data will include ICU length of stay, duration of mechanical ventilation and cost data from the hospital database for comparison of groups.

Indicate who will have access to individually identifiable private information about human subjects.

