If during the course of the study, a subject becomes alert enough to understand the study and research processes, and the LAR has provided initial consent for participation, we will obtain verbal assent (nodding) or writing (yes/no) for continuation in the study from the subject. Should the subject gain sufficient cognitive ability to provide consent while enrolled, the study personnel will obtain his/her signature on the consent form.

The same procedures will be used for those 18-20 years of age, who are considered children for federal proposals. We will follow all rules and stipulations for enrolling this age group as specified by the ORMC IRB procedures. The IRB treats those 18 years of age and older as adults who are able to provide their own consent (<http://www.orlandohealth.com/pdf%20folder/IRB%20Policies%20&%20Procedures/11-14-08/400-Children06-2008.pdf>).

E. PROTECTION AGAINST RISK

Describe planned procedures for protecting against or minimizing potential risks, including risks to privacy of individuals or confidentiality of data, and assess their likely effectiveness.

During the study, patient safety will be of highest priority and all standards of care for the ventilated patient will be followed. All study team members delivering the intervention will receive training in both simulated and clinical settings before beginning the study, and periodic re-assessment of skills is scheduled throughout the study. *The NO-ASPIRATE or usual care intervention will be stopped if clinical signs indicate the patient does not tolerate the procedure. Intolerance will be assessed by a 20% or more increase in heart or respiratory rate or a decrease in oxygen saturation below 85%.* We will train RAs in all procedures, and monitor subjects for any adverse responses. The assigned critical care intensivist physician will be notified immediately should any serious adverse events occur during the study.

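### VAC surveillance closes 2 days after the last study procedure, so subjects who stop while still ventilated (chiefly at tracheostomy) in effect enter the H2.1 percentage as VAC-negative after a shorter look

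*Combined protocol and SAP*

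**What the plan says.** The VAC paragraph under Measurement of Primary and Secondary Outcome Variables sets the window: "we will assess for VAC for 2 days beyond the last intervention". Table 1 has the same limit, and Human Subjects section B (Sources of Materials) repeats it: "Data to determine presence of VAC will be obtained daily and for 2 days after the last intervention has been delivered".

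The Endpoints paragraph ends the procedure at the first of: "1) ETT removed (extubation); 2) tracheostomy performed; 3) 14 days of enrollment; or 4) other exclusion criterion met (e.g., rescue ventilation". It also reports how often the second of these is reached: "the median time to tracheostomy is 8 days; 85% of patients on prolonged MV undergo a tracheostomy by Day 14". The same paragraph gives VAC as a reason for running the procedure for as long as 14 days, and limits analysis to subjects enrolled for 36 hours or more.

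The VAC paragraph records the outcome as positive or negative, together with the time to VAC. Analysis 2.1 takes the percentage with VAC in each group, the difference with a 95% confidence interval, and a logistic regression. Analysis 2.2 uses a Cox model and Kaplan-Meier curves. On the population, Data Analysis states: "All planned analyses will be based on the intent-to-treat (ITT) population, which consists of all subjects who have been randomized". On missing data it says only that efforts will be made to avoid them. The documents contain no fixed VAC horizon, no code for surveillance that closed early and no censoring rule.

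**The concern.** The observation window is set by how long the procedure was given, which is a post-randomisation event, and not by time since randomisation. Tracheostomy and rescue ventilation end the procedure but need not end ventilation. A VAC that begins more than 2 days after either is not looked for. With a two-valued code and a crude percentage, a subject with no VAC found by closure adds to the denominator and not to the numerator, just like a subject followed for the full period.

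Two things are at stake. First, VAC is under-counted in both arms among the longest-ventilated subjects, for whom the 14-day course was meant to be informative. Second, H2.1 includes all randomised subjects by name, but its follow-up is unequal and depends on the clinical course after randomisation. If that course differed by arm, the comparison would be biased.

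**Working it through.** **1. The plan's own figure.** The Power Analysis gives power 0.80 for a 12.7% reduction in VAC with 400 subjects. It states no control rate, so the figure cannot be reproduced from the document alone. Read as 12.7 points absolute, two-sided 0.05 and 200 per arm, power is 0.80 at a control rate of about 35.5%. The 12.7 points serve below only as a yardstick.

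**2. Which stops leave the subject at risk.**
- Extubation: a subject who stays off the ventilator loses nothing.
- Day 14: all who reach it share a horizon of 14 + 2 = 16 days.
- Tracheostomy or another exclusion criterion such as rescue ventilation: the subject may remain ventilated, and the window closes 2 days later. At the site's median tracheostomy time it closes at 8 + 2 = day 10, which is 6 days short of day 16. (The time origin of that median is not stated; enrolment is within 24 hours of intubation, so it may be up to a day out.)

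**3. Which population applies.** The 36-hour rule under Endpoints conflicts with the all-randomised definition under Data Analysis, and the two must be reconciled. The rule could remove very early stoppers, but not a subject stopped around day 8. The point stands under either population.

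**4. Most a tracheostomy subject can lose.** Assume a constant VAC hazard h of 0.01 to 0.04 per ventilated day (the documents give none) and ventilation to day 16. Risk by day t is 1 − exp(−h·t).

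| h | risk by day 10 | risk by day 16 | missed | share of day-16 events missed |
|---|---|---|---|---|
| 0.01 | 9.5% | 14.8% | 5.3 points | 5.3/14.8 = 36% |
| 0.04 | 33.0% | 47.3% | 14.3 points | 14.3/47.3 = 30% |

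**5. If ventilation ends sooner.** The Sample section gives ventilation on the units as median 4 and mean 6.2 days. Assume an exponential duration with that mean: μ = 1/6.2 = 0.161 per day, implied median 6.2 × ln 2 = 4.3 days. For a subject still ventilated at day 8, the missed risk is h·exp(8μ)·[exp(−10(h+μ)) − exp(−16(h+μ))]/(h+μ).
- h = 0.01: 0.01 × 3.634 × (0.1803 − 0.0645)/0.1713 = 2.5 points.
- h = 0.04: 0.04 × 3.634 × (0.1336 − 0.0399)/0.2013 = 6.8 points.

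The mean covers all ventilated patients on the units. Those given a tracheostomy probably run longer, so their loss should lie between these values and those in step 4.

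**6. Effect on an arm's percentage.** The share of randomised subjects in this position is not given; the 85% refers to patients on prolonged ventilation, not to all enrolled. For every 10 per 100 randomised, the arm's VAC percentage is too low by at most 0.10 × 5.3 = 0.5 to 0.10 × 14.3 = 1.4 points. By the same arithmetic, if that share differed between arms by 10 per 100, a spurious difference of at most 0.5 to 1.4 points would follow, against the planned 12.7. The documents give no reason to expect a gap of any particular size or direction.

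**The case against.** The window was chosen on a consultant's advice and follows an intervention delivered around an oral tube. A fixed window answers a different question and adds unexposed days. This is a fair defence of keeping the present count as one analysis. It does not explain why the main comparison, declared as intention-to-treat, should use it.

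Aim 2 does not rest on H2.1 alone. Time to VAC is recorded, and the Cox model for H2.2 can allow for unequal follow-up. That stands in part: no censoring rule is written, and censoring at rescue ventilation or tracheostomy may be informative, because both can reflect a worse respiratory course.

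Counting as VAC-negative is not written in the plan. That is true. It is inferred from the two-valued code, the crude percentage, the all-randomised denominator and the absence of any rule for early closure.

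A reader might go further and infer that active suction causes more early stops than sham, so that the window manufactures a benefit. The documents do not support this. Human Subjects section E says "The NO-ASPIRATE or usual care intervention will be stopped if clinical signs indicate the patient does not tolerate the procedure", but intolerance is not among the listed endpoints and nothing says such a stop is permanent. The rule covers both arms, the sham also places the catheter in the mouth, and earlier use is reported without gagging or oral trauma. ICU staff are to be blinded, so no arm difference in tracheostomy is evident either. Any arm-specific intolerance-stop rate would be pure assumption, and none is used here.

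**Conclusion.** The point holds as a flaw in how a secondary outcome is ascertained. Following the plan as written gives unequal VAC follow-up set by post-randomisation events, and subjects whose surveillance closes early in effect enter H2.1 as VAC-negative. For a day-8 tracheostomy the loss is at most about 5 to 14 points of VAC risk. It is about 2.5 to 7 points if remaining ventilation follows the units' mean. Both ranges rest on an assumed constant hazard of 1% to 4% per ventilated day. The loss falls on the long-ventilated tail and not on the typical subject.

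If it is similar in both arms, the result is under-counting and a smaller absolute difference. Bias between arms needs stopping to differ by arm; its size is unquantified and its direction unknown. It would be wrong to conclude that H2.1 is biased in favour of the intervention. The change is worth making because it is cheap and matches the plan's own intention-to-treat statement.

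**What to change.** In Table 1, the VAC paragraph and Human Subjects section B, replace the window tied to the last procedure with a fixed one. For every randomised subject, collect VAC data from the medical record through study day 16 (14 + 2), on each day of mechanical ventilation to which the VAC algorithm applies, whatever the date or reason the procedure stopped. Use this window for H2.1 and H2.2, and state the censoring rule for the Cox model. Keep the count to 2 days after the last procedure as a supportive on-treatment analysis. Reconcile the 36-hour rule with the all-randomised population, and say whether an intolerance stop ends one session or the whole course.

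The cost is wording in three places and extra chart days for subjects who stop early. The source is already in use, and no procedure or visit is added. The downside is that events after the procedure ended may dilute the effect. The supportive analysis would show this, and no gain in power is claimed.

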Our preliminary work has focused on airway management of critically ill patients who require MV. We found that development of VAP is associated with up to \$40K per case in additional costs, along with longer LOS.^{13,112} Our work has identified that frequency of oropharyngeal suction varies widely, and that the tonsil suction device is preferred.²⁶⁻²⁸ In a simulated laboratory setting, we determined that the oropharyngeal suction catheter was more effective than either a suction swab or tonsil suction device in removing oropharyngeal secretions.⁹⁹ Two oropharyngeal suction catheters are included in oral care kits used on MV patients at the study site to be used concurrently with tooth brushing; however, average use is only 0.8 per day.⁹⁵ Many patients have large volumes of oropharyngeal secretions that can be potentially aspirated.^{25,93,113} In preliminary work, we suctioned an average of 7.5 mL of secretions within a 4-hour interval, although volumes as high as 25 mL were removed.²⁵ Secretion removal can be achieved with ≤ 3 suction passes with the oropharyngeal suction catheter over an average total duration of 48.1 seconds.²⁵ We have not identified any issues when using the oropharyngeal suction catheter.^{25,93} *In a recent pilot study of 13 critically ill subjects, we found that all subjects had α -amylase present in the oral secretions, and 6 (46%) had α -amylase detected in the first tracheal sample.⁹³ The study was done to test α -amylase procedures and the intervention. A second specimen obtained one to four hours later (when ETT suctioning was needed) showed only 4 subjects (31%) with α -amylase in the tracheal secretions, and a lower value in those positive.* The study established our ability to measure α -amylase in the APH Specialty Diagnostic Laboratory with precision and quality controls. It also provided data that microaspiration frequently occurs in our study population and may be reduced with this simple intervention. Our co-investigator, [name], has studied biomarkers for microaspiration.¹¹⁴⁻¹¹⁸ He also provides oversight for the laboratory, including developing the procedures for quantifying α -amylase. These multiple preliminary studies informed our decision to focus on enhanced removal of oral secretions, using an oropharyngeal suction catheter, on a 4-hour schedule, with α -amylase as our primary outcome measure.

Design

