A prospective, 2-group, single-blind, randomized clinical trial design is planned. The design will allow us to test the impact of the NO-ASPIRATE intervention on outcomes of microaspiration and VAC.

Aims and Hypotheses

Our primary aim is to compare the effects of the NO-ASPIRATE intervention versus usual care on microaspiration in critically-ill intubated patients on MV. Patients often have high volumes of oropharyngeal secretions, and despite existing interventions, microaspiration occurs. Regular removal of secretions that accumulate in the oropharynx is intended to decrease the volume or potential load, and thus reduce microaspiration. Our working hypotheses are that subjects in the NO-ASPIRATE group will have a reduction in microaspiration as measured by the percentage of tracheal specimens that are positive for α -amylase (1.1) and *mean values of α -amylase* (1.2).

A secondary aim is to compare the effects of the NO-ASPIRATE intervention on development of VAC and duration of VAC-free days. By reducing the risk for microaspiration, VAC should be reduced. Our working hypotheses are that the subjects in the NO-ASPIRATE group will have a lower rate of VAC (2.1) and longer duration of VAC-free days (2.2). Another secondary aim is to explore changes in the ratio of α -amylase in the tracheal aspirate versus the mouth over time. Our working hypothesis is that subjects in the NO-ASPIRATE group will have a lower tracheal/oral α -amylase ratio over time (3.1).

Setting and Sample

Setting. The study will be conducted in the ICUs at Orlando Regional Medical Center (ORMC), a division of Orlando Health. ORMC is an 808-bed tertiary care facility that specializes in trauma, emergency care, cardiology, orthopedics, neurosciences, and internal medicine. The hospital serves a 5-county area in Central Florida area with a diverse population of 2.8 million people.¹¹⁹ The ICUs include Trauma (14 beds), Neuroscience (16 beds), Multi-System (10 beds), and Cardiac (10 beds). Nursing and respiratory care practices for airway management are standardized across units. The patients are managed by a team of either

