Power Analysis. We used data from our pilot work and input from our consultants to estimate sample size and attrition. *A final sample size of 400 will allow us to detect a 15% reduction in the proportion of specimens that are positive for α -amylase (primary aim) at an alpha level of .05 with a power of .87 (H1.1). The sample size will be able to detect differences in mean values of α -amylase with an effect size (d) of .25, alpha .05, and power of .80 (H1.2). Since VAC, our secondary aim, is a newer measure, we used data from recent studies to provide sample estimates. A final sample size of 400 will allow us to detect a 12.7% reduction in VAC with an alpha of .05 and power of .80 (H2.1). We will overenroll by 40% to account for attrition, for a targeted enrollment of 560 subjects.*

Procedures

Study procedures have been developed after many of the ones we have used successfully in previous studies. We also incorporated procedures described by Nseir,¹⁰⁹ Metheny,^{18,19} [name] (our consultant),^{73,80} and other researchers who have conducted intervention studies to prevent complications in MV patients.

Screening and Enrollment of Subjects. *A convenience sample of eligible subjects will be enrolled after ICU admission, within 24 hours of intubation. Our goal is to enroll subjects as soon as possible to maximize the effects of the intervention. [name] demonstrated the ability to recruit similar patients within 24 hours,^{73,120} and we will use her expertise as we implement the study.* Nseir used a 48-hour recruitment window in a study testing an intervention (control of ETT cuff pressure) on microaspiration.¹⁰⁹ We will develop a checklist to ensure that inclusion criteria are met at time of enrollment. The Project Director (PD) or research assistant (RA) will be available for 18 hours each day, 7 days per week, to facilitate enrollment. RAs will be trained registered nurses or respiratory therapists who have experience caring for patients on MV. The PD will coordinate all staffing and will develop a master schedule; flexible and variable shifts will be offered to ensure coverage for enrollment and delivering the intervention. We have a plan in place to ensure coverage and are committed to success.

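### Aim 1 tests two hypotheses, each at 0.05, without a testing order, an adjustment or a rule for success, so the error rate of the primary claim is undefined

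*Combined protocol and SAP*

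**What the plan says.** Aims and Hypotheses states one primary aim: "Our primary aim is to compare the effects of the NO-ASPIRATE intervention versus usual care on microaspiration". Two working hypotheses follow, joined by the word *and*. The first is that the treated group "will have a reduction in microaspiration as measured by the percentage of tracheal specimens" positive for α-amylase (H1.1). The second concerns mean α-amylase values (H1.2). The Preliminary Studies section names "amylase as our primary outcome measure" without saying which of the two summaries is meant.

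Power Analysis powers each hypothesis separately. For H1.1 it says "A final sample size of 400 will allow us to detect a 15% reduction in the proportion of specimens that are positive", "at an alpha level of .05 with a power of .87 (H1.1"), and it attaches the label of primary aim in parentheses to this sentence only. For H1.2 it states an effect size of d = .25, alpha .05 and power .80.

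Data Analysis gives each hypothesis its own analysis and then one general rule: "In all analyses, an alpha level of 0.05 will be used". No section gives a testing order, a multiplicity adjustment, the sidedness of the tests, or a rule for declaring Aim 1 met.

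The VAC paragraph under Measurement of Primary and Secondary Outcome Variables says "Our primary endpoint is VAC as a broad complication". Aims and Hypotheses, Power Analysis and Endpoints all place VAC under a secondary aim.

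**The concern.** With two full-alpha tests under one primary aim and no rule for combining them, a significant result on either could be reported as success on microaspiration. Nothing in the text would stop the emphasis between H1.1 and H1.2 from being settled after the results are known. The chance of a false claim for the primary aim would then be higher than the stated 0.05 suggests. The alternative reading, that both must succeed, protects the error rate but changes what the power statement means. Under either reading, a reader of the final report could not tell from the plan what counted as a positive trial.

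**Working it through.** **Inputs from the documents.** Final sample 400 at 1:1, so 200 per arm; alpha 0.05 for every test; H1.1 a 15% reduction with power .87; H1.2 d = .25 with power .80.

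**Assumptions.** The 15% is taken as 15 percentage points, from the pilot's 46% (first tracheal sample) to 31% (second sample), because Power Analysis names no rates. The correlation between the two test statistics is not given, so a range is used.

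**Step 1: the plan's power figures.**

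H1.1, two-sided, with pooled rate 0.385:
- SE under the null = √(2 × 0.385 × 0.615 / 200) = 0.0487.
- SE under the alternative = √((0.46 × 0.54 + 0.31 × 0.69) / 200) = 0.0481.
- Power = Φ((0.15 − 1.96 × 0.0487) / 0.0481) = Φ(1.136) = 0.872. This reproduces .87. A one-sided test gives 0.927, which does not.

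H1.2, with noncentrality 0.25 × √(200/2) = 2.5:
- Two-sided: Φ(2.5 − 1.96) = 0.705 (0.703 with the noncentral t), which does not reproduce .80.
- One-sided: Φ(2.5 − 1.645) = 0.804, which does.

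On these assumptions the two power figures under the same aim imply different sidedness.

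**Step 2: error if either hypothesis suffices.** Both nulls are true, each test is two-sided at 0.05, and the test statistics are bivariate normal with correlation ρ.
- Any rejection: 1 − P(|Z₁| < 1.96, |Z₂| < 1.96). At ρ = 0 this is 1 − 0.95² = 0.0975.
- False claim of benefit only: 1 − P(Z₁ < 1.96, Z₂ < 1.96). At ρ = 0 this is 1 − 0.975² = 0.0494.

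| Assumed ρ | Any rejection | Benefit direction only |
|---|---|---|
| 0 | 0.0975 | 0.0494 |
| 0.5 | 0.0907 | 0.0454 |
| 0.8 | 0.0781 | 0.0390 |
| 0.9 | 0.0704 | 0.0352 |

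For a single test the corresponding values are 0.05 and 0.025. H1.1 dichotomises the assay values that H1.2 averages, from the same tracheal specimens, so the lower rows are the more plausible.

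**Step 3: error and power if both must succeed.** The probability that both tests reject cannot exceed that of either alone, so the error is at most 0.05. Taking the stated powers at face value, joint power is 0.87 × 0.80 = 0.70 if the tests are independent. It lies between 0.87 + 0.80 − 1 = 0.67 and 0.80 whatever the correlation. No joint power is stated.

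**Step 4: H1.1 first, H1.2 only if H1.1 is significant, both two-sided at 0.05.** Familywise error is at most 0.05, and H1.1 keeps 0.872. H1.2 starts from about 0.70. The chance of winning on both is 0.872 × 0.705 = 0.61 if independent, with limits of 0.872 + 0.705 − 1 = 0.58 and 0.705.

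**The case against.** The strongest reply is that no section says either hypothesis suffices. The two are joined by *and*, and if both are required the error does not exceed 5%. This stands against any unconditional statement that the error rate is above 5%, which a reader might infer from the two full-alpha tests. It does not supply the missing rule: the plan never says both are required, and it powers each hypothesis alone.

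A second reply is that the hypotheses are directional, so only false claims of benefit matter, and with two-sided tests these stay below 5% for the pair. The arithmetic is right, but the proper comparison is the 2.5% that a single two-sided test allows in that direction. The reply also assumes two-sided tests, which the plan does not state. If H1.1 is two-sided and H1.2 one-sided, as the power figures suggest, the benefit-direction rate is 5.9% to 7.4% (correlation 0.8 to 0).

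A third reply is that Power Analysis already ties the primary aim to H1.1 and that both analyses are prespecified. This is true, and it makes the fix easy, but the label is not carried into Data Analysis.

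A reader might also infer from the VAC paragraph that VAC is a further primary outcome, and count it as a third route to success. The documents do not support this. Three sections call VAC secondary, and the sentence occurs in a paragraph on Aim 2, where it sets VAC as a whole against possible and probable VAP. A VAC result could not establish the microaspiration claim in any case, so it adds nothing to that claim's error rate.

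**Conclusion.** The concern holds in a conditional form. Aim 1 has two hypotheses at 0.05 each and no rule for combining them. If either suffices, the two-sided familywise error is about 7% to 8% at correlation 0.9 to 0.8, and at most 9.75% under independence. In the benefit direction it is about 3.9% to 4.9% (correlation 0.8 to 0) against a nominal 2.5%. If both are required, the error is controlled at 5%, but .87 overstates the power for the primary aim. The correlations are assumptions, as are the pilot rates behind the 0.872; the absence of a rule is a matter of text. This is an inexpensive improvement that should be made, not a flaw that invalidates the design. The VAC wording is a labelling slip within Aim 2 and has no bearing on the size of the error.

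**What to change.** In Data Analysis, name H1.1 as the single primary hypothesis, tested at two-sided 0.05. Test H1.2 at two-sided 0.05 only if H1.1 is significant. State that Aims 2 and 3 are secondary and carry no confirmatory claim. This takes a few sentences and leaves the sample size and H1.1's alpha and power unchanged.

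The costs should be stated openly. H1.2 is not confirmatory if H1.1 misses. Its two-sided power at 200 per arm and d = 0.25 is about 0.70, not the stated .80, before the condition on H1.1 lowers it further; the H1.2 power statement should be corrected to match.

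Splitting alpha at 0.025 each would also control the error (0.0494 if independent), but at 200 per arm it cuts two-sided power for H1.1 from 0.872 to 0.803 and for H1.2 from 0.705 to 0.602. Keeping .87 for H1.1 would need 237 per arm. The fixed order is cheaper.

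Separately, and as a wording correction only, the VAC paragraph should describe VAC as the main outcome for Aim 2 instead of the primary endpoint.
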